2 CLINICAL INVESTIGATIONAL PLAN SYNOPSIS

TITLE	Observational evaluation of the DyeVert™ Plus System
PROTOCOL NUMBER	TP-6579
STUDY PRINCIPAL INVESTIGATOR	[name]
DEVICE EVALUATED	The device evaluated in this trial is the Osprey Medical DyeVert Plus Contrast Reduction System (Model Numbers: CMW-XX and XVOFF-XXX) which consists of a Contrast Monitoring Wireless Display (CMW) and the DyeVert Plus Disposable Kit which is inclusive of a disposable single-use sterile Smart Syringe and DyeVert Plus Module.
PURPOSE	The purpose of this post-market observational study is to evaluate the DyeVert™ Plus System during standard clinical use and to quantify contrast media (CM) volume saved during manual injections in coronary angiography and interventional procedures.
STUDY OBJECTIVES	
1. Evaluate the volume (percentage) of CM saved over the total procedure, performed with manual injections2. Assessment of incidence of Serious Adverse Device Effect
STUDY DESIGN	This is a prospective, single arm, multi-center, observational clinical study of the DyeVert Plus System.
SUBJECT POPULATION	Subjects undergoing a coronary artery imaging (angiogram) for diagnostic and/or percutaneous coronary intervention (PCI) procedures are eligible to participate in this study.
TREATMENT GROUPS	This is a single-arm observational study. All enrolled subjects will have a coronary diagnostic imaging and/or PCI procedure conducted with the DyeVert™ Plus System.
CLINICAL SITES	This observational study will be conducted at up to 15 centers.
STUDY DURATION	There are no scheduled follow-up visits. Subjects will be followed through discharge.
SAMPLE SIZE	This study will enroll 118 subjects.
INCLUSION / EXCLUSION CRITERIA	
To be included in this study, subjects must meet all of the following criteria:
 
1. The subject is \geq 18 years of age2. The subject is indicated for a coronary angiogram or percutaneous coronary procedure3. The subject has baseline eGFR (as determined by the local laboratory) greater than or equal to 20 but less than or equal to 60 mL/min/1.73m²4. The subject is willing and able to provide appropriate informed consent. 
Subjects will be excluded from this trial if they meet the following criteria:
 
1. Subject is undergoing the procedure for the diagnosis of acute STEMI. Patients undergoing planned PCI to non-culprit vessel in a patient with recent STEMI and primary PCI (at least 24 hours prior) can be enrolled.

	
2. The subject is female and currently pregnant3. Subject is undergoing planned OCT analysis4. Subject is undergoing planned CTO intervention5. Subject has a planned TAVR within 72 hours of index procedure6. Subject has known coronary artery fistulas, or another condition known to require large volumes of contrast (>10mls) for each injection not allowing the possibility of contrast minimization7. Subject has a BMI >408. In the investigator's opinion, the subject is not considered to be a suitable candidate
DATA COLLECTED	
At a minimum, the following subject data will be collected or reported:
 
Pre-Procedure
 
• Demographics
◦ Age◦ Gender◦ Race and ethnicity• Vital Signs
◦ Height◦ Weight◦ BMI (calculated)• Subject medical history inclusive but not limited to:
◦ Previous Cardiovascular Disease History◦ Serum Creatinine/eGFR calculation◦ Diabetic Status◦ Anemia• Anticipated treatment plan 
Procedure Data
 
• Overall procedure data:
◦ Total time of procedure (first administration of CM to last administration of CM)◦ Access location◦ Catheter size/type◦ DyeVert Plus Disposable Kit (i.e. Smart Syringe and DyeVert Plus Module) Lot number◦ DyeVert Display (CMW) Serial number◦ CM brand/type/concentration(s)◦ Treatment type◦ Treated lesion details◦ Total fluoroscopy time◦ Additional imaging (e.g. FFR, IVUS, etc)◦ Contrast Media Information from CMW Unit: Cumulative Volume, Contrast Saved, percent Contrast Saved, set Threshold Volume amount, and percent of Physician Specified Threshold◦ Method of determining Threshold◦ Evaluation of treatment plan details◦ DyeVert System "Off" details: Reason system was turned off◦ Adverse Events

	Procedure Follow Up/Study Exit 
• All standard of care Serum Creatinine/eGFR calculations collected prior to discharge• Reason for study exit
STUDY TIMELINE	All data will be collected through discharge.

6 DATA AND QUALITY MANAGEMENT

6.1 Study Data Collection

6.1.1 Study Data Requirements

To ensure data quality and completeness, all required data will be recorded within an electronic database (EDC) provided by Osprey Medical.

6.2 Protocol Deviations

A protocol deviation is defined as a circumstance in which the Investigator or other site personnel did not conduct the trial according to the protocol, applicable laws/regulations, or any study agreements (i.e. Clinical Trial Agreement or Investigator Agreement).

Protocol Deviations will be documented on the Protocol Deviation eCRF. Protocol deviations are reportable to the Institution's governing Institutional Review Board (IRB) during the annual reporting process, unless otherwise directed by the governing IRB requirements or as the specific circumstance dictates.

6.3 Investigator Certification

Osprey Medical certifies that the investigator will fully execute the Osprey Medical Investigator Agreement for this DyeVert Plus Trial.

6.4 User Training

Physician investigators will be specialists in interventional cardiology. Primary users using the DyeVert Plus System will undergo training on set-up and use of the system. Auxiliary personnel, such as catheter laboratory technicians, may also be trained in system use. The training will include on-site training, but may also be supplemented with additional training. Training materials such as IFU and training presentations will be provided. All training will be conducted by Osprey Medical representatives and/or Osprey Medical-designated representatives. If primary users have extensive use of the DyeVert product, training may be tailored to represent need-based training.

7 STATISTICAL METHODS AND DATA ANALYSIS

7.1 Analysis of Primary Effectiveness Objective

The primary endpoint of the study is the mean percentage of CM volume saved. Analysis will be based on a one sample t-test. The formal statistical test will be based on a one-sided t-test against a fixed null hypothesis. The null and alternative hypothesis to be tested is:

$$H_0: \mu_{diverted} \leq 30\%$$

$$H_a: \mu_{diverted} > 30\%$$

where $\mu_{diverted}$ is the mean percentage measured volume saved. Successful rejection of the null hypothesis will demonstrate that the percentage of volume saved is statistically greater than 30%.

To account for the variation in contrast savings by procedure type, a supplementary analysis will be performed using a model to adjust for procedure type (PCI vs diagnostic). An additional analysis adjusting for physician will also be employed if deemed appropriate based on number of physicians and number of cases per physician.

7.1.1 *Sample Size Considerations*

The mean total contrast volume saved is expected to be at least 35%. Based on a sample size of 100 subjects and a one-sided 0.025 alpha level, greater than 80% power will be provided for a standard deviation of 16. A larger mean or smaller standard deviation would provide additional power.

To account for the possibility of unavailable contrast savings data or incorrect usage of the device, a 15% attrition rate will be utilized. A total of 118 subjects will be enrolled to obtain approximately 100 evaluable subjects. The following instances indicate subjects deemed unevaluable for the primary analysis.

- The DyeVert Reservoir was inadvertently turned off due to user error for > 1 injection.
- The DyeVert Reservoir was turned OFF for >1 injection due to an adverse event, not related to the device.
- The CMW did not provide contrast accounting details at the end of a case due to device deficiency.
- A contrast accounting error due to user error occurs for > 1 injection as defined in the procedure case report form.
- The treating physician determines that a blue tooth disconnection occurred resulting in inaccurate contrast accounting.

7.2 *Subgroup Analyses*

A subgroup analysis of the primary endpoint will be performed based on access approach (radial versus femoral), body mass index (BMI), physician user and procedure type. For BMI, subgroups will be defined those with $BMI < 30 \text{ kg/m}^2$ versus those $\geq 30 \text{ kg/m}^2$. A two-sample t test will be performed to compare the primary endpoint between groups at the nominal 0.05 alpha level. For grouping physicians in more than two groups, an ANOVA model will be used.

7.3 *Additional Statistical Considerations*

The primary analysis of endpoints will be based on the population of subjects with evaluable data for that endpoint. Cases deemed unevaluable in the primary analysis will be summarized in a listing and a second analysis will be performed inclusive of these cases. Sensitivity analyses for missing data may be performed if warranted. In the event normality assumptions of statistical models are not met, logarithmic transformations or non-parametric methods will be employed. All data will be summarized by descriptive statistics, using the mean, standard deviation, median, interquartile range, or percentages, numbers of patients with events, etc. and the associated 95% confidence intervals, as appropriate.

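### The Bluetooth exclusion in 7.1.1 rests on the treating physician's unconfirmed judgement, so the one-sided test against 30% could be biased, plausibly upward

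*Combined protocol and SAP*

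**What the plan says.** The design and test are in the Synopsis and section 7.1: "This is a prospective, single arm, multi-center, observational clinical study of the DyeVert Plus System"; "The primary endpoint of the study is the mean percentage of CM volume saved"; "The formal statistical test will be based on a one-sided t-test against a fixed null hypothesis". The null value is 30%.

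Section 7.1.1 then lists five reasons for calling a subject unevaluable for the primary analysis. The fifth is: "The treating physician determines that a blue tooth disconnection occurred resulting in inaccurate contrast accounting".

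Section 7.3 gives the list its force: "The primary analysis of endpoints will be based on the population of subjects with evaluable data for that endpoint". The same section commits to listing the unevaluable cases and to a second analysis that includes them.

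The outcome itself is a device readout. The Synopsis, under Data Collected, names "Contrast Media Information from CMW Unit: Cumulative Volume, Contrast Saved, percent Contrast Saved".

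**The concern.** The fifth reason is built differently from the other four. Three of those need more than one affected injection, and one of the three also points to a definition in the procedure case report form. The remaining one applies when the CMW gave no accounting at the end of the case because of a device deficiency. The Bluetooth reason concerns accounting that is inaccurate rather than absent, so it can remove a case for which a percent saved exists. It depends on the treating physician's determination. It states no injection count, form definition, device record, timing rule or independent check.

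The study has one arm, the CMW reports the percent saved, and the available text describes no masking of the physician to it. The decision may therefore be taken with the outcome in view. If low readings are questioned more readily than high ones, the analysed mean rises and the test rejects too often when the true mean is 30%. The planned margin is only 5 points (35% against 30%), so a shift of 1 to 2 points would matter.

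**Working it through.** **Inputs from 7.1 and 7.1.1.** Null mean 30%, expected mean 35%, SD 16, one-sided alpha 0.025, 100 evaluable, 15% attrition, 118 enrolled.

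**The plan's own figures.** The noncentrality is (35 − 30)/16 × √100 = 3.125. The noncentral t distribution with 99 degrees of freedom gives 87.2% power, which agrees with the stated figure of more than 80%. Enrolment is 100/(1 − 0.15) = 117.6, rounded up to 118, which also agrees. The allowance is 118 − 100 = 18 cases for all five reasons together. The sample size is not in dispute.

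**Effect of exclusions.** I drew 118 values from Normal(30, 16), removed k of them under a stated pattern, and tested the rest against 30 at one-sided 0.025, with 20,000 simulated trials per cell. The normal shape, the values of k and the patterns are assumptions, because the documents give no frequency for Bluetooth exclusions.

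Type I error:

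| Pattern of exclusion | k = 3 | k = 6 | k = 12 |
|---|---|---|---|
| Unrelated to saving | about 2.5% | about 2.5% | about 2.5% |
| Lower-half cases twice as likely | 2.9% | 3.4% | 4.8% |
| Lower-half cases three times as likely | 3.2% | 4.2% | 6.3% |
| All from the lower half | 3.9% | 6.1% | 14.2% |
| All from the lowest third | 4.7% | 8.9% | 25.6% |

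Repeat runs move these by a few tenths of a point in most cells, and by up to about one point in the largest.

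**Check on the shift in the mean.** In the lower half of a normal distribution the average shortfall from the mean is 0.798 × 16 = 12.8 points. Removing k such cases raises the remaining mean by about k × 12.8/(118 − k):
- k = 6: 76.8/112 = 0.7 points
- k = 12: 153.6/106 = 1.4 points

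The simulation gives the same values. For the lowest third it gives 0.9 and 2.0 points.

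**What the second analysis would show.** With 12 exclusions all from the lower half, the primary test rejected while the all-cases test did not in about 12% of simulated trials. Section 7.3 does not say how such a result would be reported.

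**The case against.** The strongest reply is that the criterion is not a licence to drop a disappointing reading. It requires that a disconnection took place and that inaccurate accounting resulted. Section 7.3 then puts each excluded case in a listing and repeats the analysis with those cases included, so selective removal would be visible. No passage links Bluetooth loss to low savings; a disconnection could misstate the saving in either direction.

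Much of this stands. A reader might infer that the primary test is biased upward as written. The documents do not support that: they give neither a count of such exclusions nor any relation to the saving, and unrelated exclusions leave the error rate at its nominal level. A reader might also take the 14% to 26% cells as the likely size. Those cells assume that 12 cases leave for this one reason and that none comes from the upper part of the distribution, whereas the allowance of 18 is shared among five reasons. That the physician sees the percent saved is a natural inference from the design, not a statement in the text. Sections 3 to 5 and the case report form are not available, so a definition there cannot be ruled out.

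The reply does not remove two gaps. Nobody is named to confirm the disconnection. Nor does the plan say what becomes of the 30% claim if the primary and inclusive analyses disagree.

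**Conclusion.** The point holds as a weakness in the exclusion rule, not as a demonstrated bias. An unconfirmed judgement by the device user can take a case with a reading out of the primary set, and the effect on the test could be upward. At a true mean of 30% and SD 16, type I error is:
- about 2.5% if exclusion is unrelated to saving;
- about 3% to 6% for 3 to 12 exclusions under moderate selection (two to three times as likely from the lower half);
- about 4% to 26% under total selection.

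The selection patterns and counts are assumed. The listing and second analysis in 7.3 are a partial safeguard: they would expose a disagreement but do not govern the conclusion. Tightening the rule is a cheap improvement worth making.

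**What to change.** Reword the fifth reason in 7.1.1 so that a Bluetooth exclusion needs all of the following:
- a disconnection documented on the procedure case report form or in available device or CMW records;
- more than one injection affected, as in the neighbouring criteria;
- confirmation before analysis by existing study staff who are unaware of the percent saved.

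Add to 7.3 that the claim of more than 30% is reported together with the planned inclusive analysis and is qualified if the two disagree.

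The rule should not depend on the disconnection being entered before the end-of-case figure is read. That would force cases whose disconnection was recognised late into the primary endpoint with values known to be wrong.

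The cost is a little more documentation, and a few cases with unconfirmed disconnections stay in the primary set. The sample size does not change; if all 118 were analysed, power at a mean of 35% and SD 16 would be 92.0%.

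### Section 7.2 compares access and BMI groups without adjusting for procedure type and uses BMI only as a cut at 30; one exploratory model would separate these differences from PCI-diagnostic mix

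*Combined protocol and SAP*

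**What the plan says.** Section 7.2 plans subgroup analyses of the primary endpoint "based on access approach (radial versus femoral), body mass index (BMI), physician user and procedure type". The method is: "A two-sample t test will be performed to compare the primary endpoint between groups at the nominal 0.05 alpha level". More than two physician groups are handled by ANOVA. No covariate is named, and BMI enters only as two groups, below 30 and 30 or above.

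Section 7.1 has two covariate models for the primary endpoint. The first is firm: "To account for the variation in contrast savings by procedure type, a supplementary analysis will be performed using a model to adjust for procedure type". The second is conditional: "An additional analysis adjusting for physician will also be employed if deemed appropriate based on number of physicians and number of cases per physician". Neither contains access or BMI, and neither is linked to the comparisons in 7.2. Section 7.3 covers evaluability, missing data and non-normality, and adds no multivariable model and no continuous BMI analysis.

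The synopsis lists "Access location" and "Treatment type" among the procedure data and a calculated BMI among the vital signs. Subjects with a BMI above 40 are excluded.

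**The concern.** The plan itself expects savings to differ between PCI and diagnostic cases, then compares access and BMI groups without using that variable. If radial and femoral cases contain different shares of PCI, the raw difference mixes the two factors. Listing procedure type as a further subgroup does not adjust the other comparisons.

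Because each contrast comes with a test at 0.05, a reader may credit access route or body size with a difference that reflects the share of PCI cases. Separately, if savings change gradually with BMI, the split makes the trend harder to see. Only the nominal subgroup results are at stake.

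**Working it through.** **Inputs.** From Section 7.1: 100 evaluable subjects, SD 16, expected mean 35%, null 30%, one-sided 0.025, 15% attrition. From Section 7.2: two-sample t test at 0.05, taken as two-sided because the sides are not stated. Group sizes, PCI shares, the PCI-diagnostic gap, the BMI distribution and physician clustering are not in the documents. All values used for them are assumptions.

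**1. The plan's own figures.** Noncentrality = (35 − 30) / (16/√100) = 3.125 on 99 df, which gives 87.2% power and agrees with the stated figure of more than 80%. Enrolment: 100/0.85 = 117.6, rounded up to 118. Both reproduce, and the plan gives no figure for the subgroup tests.

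**2. Access comparison, no true access effect.** Bias of the raw difference = (difference in PCI share) × (PCI-diagnostic gap). For a 60:40 split, SE = 16 × √(1/60 + 1/40) = 3.27. Rejection comes from the noncentral t distribution (98 df, noncentrality bias/SE):

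| PCI-share difference | Gap (points) | Bias | Bias/SE | t test rejects |
|---|---|---|---|---|
| 0 | any | 0 | 0 | 5.0% |
| 15 points | 5 | 0.75 | 0.23 | 5.6% |
| 15 points | 8 | 1.2 | 0.37 | 6.5% |
| 15 points | 10 | 1.5 | 0.46 | 7.4% |
| 30 points | 5 | 1.5 | 0.46 | 7.4% |
| 30 points | 8 | 2.4 | 0.73 | 11.3% |
| 30 points | 10 | 3.0 | 0.92 | 14.9% |

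With an 80:20 split, SE = 16 × √(1/80 + 1/20) = 4.0, and the last two rows become 9.1% and 11.5%. Simulations of 4,000 trials per case agree with the table. In the same simulations a linear model with access, procedure type and continuous BMI rejects in about 4-5% of trials.

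**3. The same model when physicians differ.** Step 2 assumes no physician effect. Now assume an outcome ICC of 0.10, moderate to strong clustering of access by physician (0.3 to 0.6), 8 to 25 physicians, PCI shares 35% and 65%, and a 5-point gap. The model without physician then rejects in about 6-13% of trials, and the t test in about 8-16%. The model helps but does not hold 5%.

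**4. The BMI cut.** The share of information on a linear trend kept by a cut is the squared correlation between BMI and the indicator for 30 or above. For a normal BMI truncated to 16-40:

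- mean 28, SD 5: 0.617
- mean 29.5, SD 5: 0.653
- mean 31, SD 5: 0.661
- mean 29.5, SD 4: 0.640

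The loss is therefore 1 − 0.661 = 34% to 1 − 0.617 = 38%. For a linear relation that produces a given difference between the two BMI groups, power in the proposed model against the split test is:

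- 3 points: 20-22% against 15-16%
- 5 points: 48-50% against 31-34%
- 8 points: 88% against 67-72%

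These power figures combine two changes, the adjustment and the continuous term. If the truth is a 5-point step at 30, the order reverses: 35% for the split against 25% for the continuous term.

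**The case against.** The plan makes no claim about independent access or BMI effects. Its objectives are contrast saved and serious adverse device effects, the subgroup level is called nominal, and raw means properly show how savings look in each group. One sentence labelling 7.2 as descriptive would prevent most misreading. The harm is also assumed: no passage gives a PCI share by access route or a PCI-diagnostic gap, and under mild values the distortion is negligible. The BMI gain depends on a roughly linear relation that nothing in the documents establishes.

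All of this stands, and it sets the weight of the point: an improvement to exploratory analyses. It does not remove the case for the model, because 7.1 already treats procedure type as a source of variation and the data are being collected.

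A reader might infer that the added model would show whether differences go beyond case mix altogether. It would not. It contains procedure type and BMI, but not catheter size, lesion details or additional imaging, which are also collected, and it contains physician only if the 7.1 condition is met. Nor does adjustment guarantee a 5% error rate once physicians differ (step 3).

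**Conclusion.** The point holds as a low-severity improvement. The planned contrasts cannot separate access or BMI from PCI-diagnostic mix, and nothing in 7.1 or 7.3 closes that gap. The inflation of the access test runs from negligible (5-7%) to moderate (about 10-15%). The upper range needs both a 30-point share difference and an 8-10 point gap. The 34-38% loss from the BMI cut applies only to a roughly linear relation.

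Three stronger readings are not supported:

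- That the t tests are invalid: they correctly compare raw means.
- That a case-mix imbalance exists: the documents neither show nor exclude one.
- That the main result is affected: the primary test and the 118 enrolled are untouched.

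A null adjusted result would not show that a difference is absent either. With 100 subjects even the unadjusted 95% interval for access is about ±6.5 points at 60:40 (1.98 × 3.27) and ±7.9 at 80:20 (1.98 × 4.0).

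**What to change.** Keep the 7.2 means and tests, including the BMI split, and label them descriptive. Add one exploratory linear model for percent saved with access approach, procedure type (PCI vs diagnostic) and continuous BMI. Report estimates with 95% CIs as differences adjusted for procedure type and BMI, not as independent or causal effects. Add physician, preferably as a random effect, under the condition 7.1 already sets. If physician is left out, state that confounding by physician may remain.

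**Cost.** One or two sentences, one more table and no new data. Without physician, the access standard error in the simulated cases ran from about 4% smaller to 7% larger than unadjusted. Physician costs more: up to 15 centers and 100 evaluable subjects mean about 100/15 = 6.7 per center, so many physicians may have few cases. With 8-25 physicians and ICC 0-0.10 (assumed), a random effect widened the access standard error by a median of 1-9% up to moderate clustering and 4-21% with strong clustering. Fixed effects widened it by 19-42% with moderate and 54-86% with strong clustering. The continuous BMI term assumes linearity. Since the split does better for a step at 30, both should be reported.

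### The physician comparison in section 7.2 names no adjustment for procedure type, so a different PCI/diagnostic mix can pass for an operator difference

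*Combined protocol and SAP*

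**What the plan says.** Section 7.2 lists four subgroup factors for the primary endpoint: access approach, BMI, physician user and procedure type. Two-group comparisons use a two-sample t test at a nominal 0.05 level. For physicians it adds: "For grouping physicians in more than two groups, an ANOVA model will be used". No covariate is named for either method.

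Section 7.1 plans two supplementary analyses of the primary endpoint. One is a model adjusting for PCI versus diagnostic procedure, and the stated reason is that savings are expected to vary by procedure type. The other is conditional: "An additional analysis adjusting for physician will also be employed if deemed appropriate based on number of physicians and number of cases per physician".

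On size, section 7.1 plans about 100 evaluable subjects, and the synopsis says: "This observational study will be conducted at up to 15 centers". The documents state neither the number of physicians nor the expected PCI share.

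**The concern.** The plan treats procedure type as a source of variation in the endpoint, then compares physicians without it. Operators in one study can differ a good deal in how much of their work is diagnostic and how much is PCI. If savings differ by procedure type, part of that difference in mix moves into the physician means, and the F test cannot tell it from an operator effect.

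The two analyses in 7.1 do not close the gap. Both ask whether the overall mean holds up after adjustment. Neither asks whether physicians differ once procedure type is accounted for.

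What is at stake is the reading of one stated subgroup result. A positive physician finding could be reported as dependence on the user when it reflects case mix.

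**Working it through.** **1. The plan's own figure.** The inputs are in section 7.1: 100 evaluable subjects, a one-sided alpha of 0.025, an SD of 16, an expected mean of 35% and a null value of 30%. The stated result is: "greater than 80% power will be provided for a standard deviation of 16". The noncentrality is (35 − 30)/16 × √100 = 3.125 on 99 degrees of freedom. Power is 87.2%, which agrees with the stated figure. Enrollment is 100/0.85 = 117.6, rounded up to 118, which also agrees. I therefore use N = 100 and a total SD of 16 below.

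**2. Assumptions that the documents do not supply.**
- The number of physicians is k = 10 or 15, with m = 100/k cases each. The 15 matches the ceiling on centers at one operator per center.
- There is no true physician effect.
- The PCI/diagnostic difference is d = 5, 10 or 15 points.
- Each physician's PCI share is uniform between 0 and 1, which has variance 1/12.

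**3. Size of the spurious physician effect.** Case mix alone creates a between-physician variance of d²/12. As a share of total variance, ρ = (d²/12)/256. The unadjusted F test rejects with probability approximately

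P( F(k−1, 100−k) > Fcrit / [1 + mρ/(1−ρ)] ).

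Fcrit is 1.99 for k = 10 and 1.81 for k = 15.

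| d (points) | d²/12 | Spurious SD (points) | ρ | Rejection, k = 10 | Rejection, k = 15 |
|---|---|---|---|---|---|
| 5 | 2.08 | 1.4 | 0.008 | 7.3% | 6.7% |
| 10 | 8.33 | 2.9 | 0.033 | 16.5% | 13.7% |
| 15 | 18.75 | 4.3 | 0.073 | 36.5% | 30.1% |

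Worked line for k = 15 and d = 10: 1 + 6.67 × 0.033/0.967 = 1.22; 1.81/1.22 = 1.48; P(F(14, 85) > 1.48) = 13.7%.

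**4. Check by simulation, with and without procedure type.** Each scenario had 1,500 runs with unequal caseloads, no physician effect and a 5% level.

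| Scenario | ANOVA | ANOVA + procedure type | Random intercept | Random intercept + procedure type |
|---|---|---|---|---|
| k = 15, no mix difference | 5.0% | 5.3% | 4.1% | 3.7% |
| k = 15, d = 10 | 13.8% | 4.7% | 12.3% | 3.7% |
| k = 15, d = 15 | 30.3% | 4.9% | 31.8% | 3.3% |
| k = 10, d = 10 | 15.9% | 5.2% | 15.1% | 3.9% |

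The simulated ANOVA rates agree with step 3. Procedure type brings the rate back to nominal in either kind of model. A random intercept without it does not.

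**5. What adjustment costs in power.** With k = 15, a true physician effect at an intraclass correlation of 0.10 (physician SD 16 × √0.10 = 5.1 points) and no mix difference, power is 41.8% unadjusted and 41.3% adjusted. At 0.20 (SD 7.2 points) it is 76.8% and 76.2%. Residual degrees of freedom fall from 85 to 84.

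**The case against.** The strongest reply is that this is one of four subgroup factors tested at a nominal level, outside the primary hypothesis. The text says only an ANOVA model, which could carry procedure type; that it has a single factor is an inference from silence. Section 7.1 already plans a procedure-type model and a conditional physician-adjusted one. The physician count, the mix and the procedure difference used here are all assumed, and 15 centers is a ceiling. All of this is fair. It limits the point to a low-cost improvement and makes the rejection rates illustrations rather than forecasts. It does not supply the missing covariate, because the 7.1 models answer a different question.

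A reader might infer more, and the documents do not support it:

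- *That ANOVA cannot tell operator differences from chance at this size.* It can. With balanced mix the F test holds its 5% level. With 15 physicians and equal caseloads its power is about 42% at a physician SD of 5.1 points and 79% at 7.2. Power is low for modest effects because N is about 100, not because ANOVA was chosen.
- *That a random-intercept model would solve the problem.* With 15 physicians its power is practically the same (41.5% and 76.3%, against 41.8% and 76.8% in the simulation), and step 4 shows that without procedure type it is confounded to about the same degree.
- *That physicians will be pooled after their results are seen.* The sentence can simply mean a t test for two physicians and ANOVA for more. The absence of a grouping rule is missing detail, not evidence of a data-driven choice.

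**Conclusion.** The point holds as a gap in 7.2. The physician comparison names no adjustment for a factor that 7.1 itself expects to matter. With no true physician effect and PCI shares uniform across physicians, the unadjusted test rejects about 7% of the time at a 5-point procedure difference. The rate is about 14% to 17% at 10 points. At 15 points it is about 30% with 15 physicians and 36% with 10. The simulated rate with procedure type in the model is about 5%. If physicians have similar mixes, or savings barely differ by procedure type, the inflation is small.

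The comparison is exploratory. The one-sample primary test and its sample size are unaffected.

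**What to change.** In section 7.2, state that physicians are compared in a model for percent contrast saved with procedure type (PCI versus diagnostic) as a covariate, and that procedure-type-adjusted physician differences are reported. Apply the same model if there are only two physicians or physician groups, since the t test has the same gap. The cost is one degree of freedom and one line of code. Treatment type is already in the procedure data listed in the synopsis, so nothing new is collected. One caution for reporting: for a physician with only PCI or only diagnostic cases, the adjusted value rests on a procedure-type difference estimated from the other physicians.

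A physician random intercept, with a between-physician SD and shrunken means, is an optional descriptive addition and not a correction. With 15 to 30 physicians and a true between-physician SD of 5 points, simulation gave a median 95% interval for that SD of about 0 to 10.5 points and an estimate of exactly zero in 13% to 18% of trials. If it is used, it also needs procedure type as a fixed effect.
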